## 8.2. Bayesian Dose Escalation Analyses

### 8.2.1. Overview of Planned Bayesian Dose Escalation Analyses

The Bayesian Dose Escalation analyses will be based on the PK population, unless otherwise specified.

Table 7 provides an overview of the planned Bayesian analyses, with further details of data displays being presented in Appendix 11: List of Data Displays.

**Table 7 Overview of Planned Bayesian Analyses**

Endpoint / Display Type	Untransformed						Log-Transformed								
	Stats Analysis			Summary			Individual		Stats Analysis			Summary		Individual	
	T	F	L	T	F		F	L	T	F	L	T	F	F	L
AUC[0-t], AUC[0-24], AUC[0-8]x3, Cmax				Y	Y		Y	Y	Y						

**NOTES :**

- T = Table, F = Figure, L = Listing, Y = Display generated.
- Stats Analysis = Represents TFL related to any formal statistical analyses (i.e. modelling) conducted.
- Summary = Represents TF related to any summaries (i.e. descriptive statistics) of the observed raw data, posterior distribution data and predictive data about future hypothetical subjects.
- Individual = Represents FL related to any displays of individual subject observed raw data.

### 8.2.2. Planned Bayesian Statistical Analyses

**Table 8 Bayesian Statistical Analyses**

Bayesian Statistical Analyses
Endpoint(s)

 
• AUC[0-t] where t varies depending dose and Cmax for Part 1 single dose phase
 
• AUC[0-24] which is calculated as AUC[0-8]x3, Cmax for Part 2 repeat dose phase
 

Model Specification

To guide dose selection, Bayesian posterior inferences about population probability distributions of model parameters of PK parameters will be assessed by using the following power model:
 $y = \exp(\theta_1 + \varepsilon) \cdot \text{dose}^{\theta_2}$ 
where y denotes the PK parameter being analyzed. The <math>\theta_s</math>, s=1,2, in the power model will be estimated by linear regression of the loge-transformed PK parameters on loge dose levels.
 $\log(y_{ij}) = \theta_1 + \theta_2 \cdot \log(d_{ij}) + \varepsilon_{ij} \quad (1)$ 
where
 
 
• <math>y_{ij}</math> is the observed or predicted log-PK variable of the j-th dose <math>d_{ij}</math> administered to the i-th subject. In particular, it is an AUC (AUC[0-t] for single dose, and AUC[0-24] for repeat dose) or a Cmax, as applicable.
 
• <math>\theta_1, \theta_2</math> are population intercept and slope, respectively.
 

### Bayesian Statistical Analyses

- $\epsilon_{ij}$  is a random error term, with mean zero and variance  $\sigma^2$ .

In general, Bayesian inference seeks to quantify the probability distributions of model parameters such as the  $(\theta_1, \theta_2, \sigma)$  defined in Equation (1). The present inference will incorporate a normal-Half-Normal prior distribution, to express the prior information about the parameters  $(\theta_1, \theta_2, \sigma)$ . Due to limited information available about the GSK3342830 compound, an informative prior with large variance will be used. For ease of parameterization for the normal distribution in computer programming, use  $\nu = \sigma^{-2}$  as the precision. Model parameters are assumed *a priori* to be independent.

**Table 9** Prior Distributions

Model Parameter	Prior
$\theta_1$ (intercept)	~ Normal(-1, precision= $10^{-6}$ )*
$\theta_2$ (slope of log-dose)	~ Half-Normal(0, precision= $10^{-5}$ , lower=0)*
$\nu$ (precision)	~ Gamma(1, iscale=5)*

All model parameters are *a priori* independent.

\*SAS Version 9.4 will be used for the Bayesian analysis, specifying the normal distribution using mean and precision. Because of the assumption that population mean PK parameter values increase as a higher dose is administered, let  $\theta_2$  have a Half Normal prior distribution truncated at 0 to guarantee the positivity of  $\theta_2$ . Simple linear regression, with maximum likelihood estimation, on available data at dose escalation will be used to estimate the model parameters  $(\theta_1, \theta_2, \nu)$ , thus providing the initial values for model parameter estimation by Bayesian approach; however, if insufficient data are available for estimation, (1, -1, 0.2) will be used as the initial values for  $(\theta_1, \theta_2, \nu)$ . Furthermore, the scale and shape parameters of the precision prior Gamma function are chosen to attain  $E(\nu)=0.2$  and  $\text{Var}(\nu)=0.04$ . Two chains will be run for the estimation of each parameter.

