4.2. Treatment Arms and Duration

[figure not shown]
Part 1: Single Dose Escalation in Healthy Adult Subjects

Part 1 is planned to include 6 dose level cohorts. Additional doses (1 per cohort) may be evaluated to further understand the study drug. The planned starting GSK3342830 dose in Part 1 is 250 mg administered as a single IV infusion. The dose is planned to increase in subsequent cohorts to 500, 1000, 2000, 4000, and ≤ 6000 mg IV as shown in Figure 1. Doses >6000 mg may be administered if the predicted C_{max} exposures will not exceed the NOAEL.

On Day 1, before study drug administration, subjects will be randomized to treatment with either GSK3342830 or placebo in a 3:1 ratio. As a safety precaution, all Part 1 cohorts will be split into 2 sub-cohorts for sentinel dosing. In each cohort, the first 2 subjects will receive either GSK3342830 or placebo (1 active/1 placebo). Dosing in the remaining 6 subjects (5 active/1 placebo) in that cohort will occur at least 24 hours later based on the safety results from the first sub-cohort. Study assessments will be performed as indicated in the Time and Events Tables (Section 7.1).

Doses are planned to escalate in a sequential fashion contingent on the safety, tolerability, and PK profile of approximately 4 subjects who received active treatment in the previous cohort. The evaluated subjects should be followed for a minimum of 48 hours after dosing. Dose escalations or reductions will progress with modifications based on the preliminary safety, tolerability, and PK data from the preceding cohorts.

Figure 1 Part 1 Single Dose Escalation Study Design Schematic

Note: Figure shows illustration of the planned doses, which may be switched, changed, or cancelled based on preliminary safety, tolerability, and pharmacokinetic data from preceding cohorts.

The AUC from time zero to the last quantifiable concentration after dosing (AUC[0-t]) and C_{max} observed in the human subjects in this study at each single dose will be compared with the systemic NOAEL animal exposure values in order to determine the magnitude of dose escalation.

The dose escalation strategy is based on the following 2 principles:

- Bigger dose escalation steps will be allowed at lower systemic exposures as the expected risk of AEs at these exposures is low. The magnitude of dose escalation steps will be progressively restricted at higher exposures.

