### 3. PLANNED ANALYSES

#### 3.1. Interim Analyses

No formal interim analysis is planned for this study. However, one may be conducted in the event of clinically significant safety or PK findings. All preliminary safety, tolerability, and available PK data will be reviewed internally at GSK and with the clinical study site before each dose escalation in Part 1, before initiation of Part 2, and before each dose escalation in Part 2.

The relationship between dose and plasma GSK3342830 exposure, and associated variability will be characterized by a power model once data are available from 3 dose levels. Prior to that, prediction of the human exposure at the next dose will be based on population PK modeling (if feasible) or on the assumption of dose–exposure proportionality (i.e., doubling the dose gives an approximate doubling of exposure). If prior PK results show less than proportional increase in exposure with increasing dose, the prediction will be based on the assumption that the fold exposure increase to fold dose increase ratio will be the same with the current dose escalation as it was with the previous one. If prior PK results show more than proportional increase in exposure with dose, subsequent dose escalations will not be higher than 3-fold. The power model will be updated as data become available throughout the study. During dose escalation, Bayesian inferential probability that a group mean will have AUCs (AUC[0-t] for single dose and AUC[0-8]x3 as AUC[0-24] for repeat dose) and Cmax values greater than 2875 h•µg/mL and 2270 µg/mL (mean exposures at the NOAEL dose in the rat and monkey), respectively, and Bayesian predictive probability that an individual will have AUC(0-24) and Cmax values greater than 3460 h•µg/mL and 2590 µg/mL (maximum exposures at the NOAEL dose in the rat for AUC and the monkey for Cmax), respectively, may be calculated for the next dose level and used together with safety and tolerability data to aid the next dose selection.

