**Bayesian Statistical Analyses**

observed data.

- The range of possible doses: 250, 500, 1000, 2000, 4000 and 6000 mg for Part 1 and 1000, 2000, 4000 mg for Part 2.
  - At each chain of the MCMC algorithm in the SAS program (as described above), we will obtain an estimate for the mean AUC[0-t] or Cmax at each dosing level (as in the previous bullet for Part 1) with a 90% CrI using the 5th and 95th percentiles. This will be calculated as found in the model formulation (1) using the sampled parameter values.
  - These point estimates will be displayed on a figure with the dots connected. If the associated posterior distributions for the predicted responses at the dose levels are skewed then the point estimates used to generate the dose response curve plot will be generated using the median as a measure of central tendency. The 5th and 95th percentiles will still be used for the 90% CrI about the parameter.
  - The observed data will be overlaid on this curve at the doses which were explored.
- The Bayesian inferential probability that mean AUC[0-t] and Cmax values will be greater than 2875 h.µg/mL and 2270 µg/mL (maximum exposures at the NOAEL dose in the rat for AUC and the monkey for Cmax), respectively, will be calculated for each dose level in Part 1.
  - The Bayesian predictive probability that an individual subject will have AUC[0-t] and Cmax values greater than 3460 h.µg/mL and 2590 µg/mL (maximum exposures at the NOAEL dose in the rat for AUC and the monkey for Cmax), respectively, will be calculated for each dose level in Part 1.

All the outputs discussed above and listed below are used together with safety and tolerability data to aid the next dose selection.

The mean, median, and 5th and 95th percentiles (90% CrI) for each model parameter and prediction will be tabulated.

Figures will be produced for posterior dose-response model for AUC[0-t], and Cmax (with 90% CrI), respectively as discussed above in inference bullet.

A Listing for PK parameters AUC[0-t] and Cmax in Part I single dose phase will be provided.

In addition, the above listed inferences and predictions will be performed for PK parameters AUC[0-24] and Cmax in Part 2 repeat dose phase. The corresponding tables, figure and listing listed above will also be produced.

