**Sensitivity and Supportive Statistical Analyses**

Not applicable.

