### **8.2.3. Deviations from RAP Planned Analysis**

To ensure transparency, any deviations from the above analyses will be documented in a log appended to the CSR. These deviations may include (although are not limited to) algebraically different model parameterizations or changes in the prior structure to support convergence of the parameter estimations in SAS. These possible issues and solutions for them are discussed above in the appropriate sections.

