Bayesian Dose Escalation					
3.14	PK Parameter	PK_T2	Summary of Model Parameters for Part 1 - Posterior Distributions		DE [1]
3.15	PK Parameter	PK_T2	Summary of Model Parameters for Part 2 - Posterior Distributions		DE [1]
3.16	PK Parameter	PK_T3	Summary of PK Parameters for Part 1 - Bayesian Prediction of Individual Subjects		DE [1]
3.17	PK Parameter	PK_T3	Summary of PK Parameters for Part 2 - Bayesian Prediction of Individual Subjects		DE [1]
3.18	PK Parameter	PK_T4	Summary of PK Parameters for Part 1 - Bayesian Predictive Probability		DE [1]

Pharmacokinetic : Tables					
No.	Population	IDSL / TST ID / Example Shell	Title	Programming Notes	Deliverable [Priority]
3.19	PK Parameter	PK_T4	Summary of PK Parameters for Part 2 - Bayesian Predictive Probability		DE [1]
3.20	PK Parameter	PK_T4	Summary of PK Parameters for Part 1 - Bayesian Inferential Probability		DE [1]
3.21	PK Parameter	PK_T4	Summary of PK Parameters for Part 2 - Bayesian Inferential Probability		DE [1]
3.22	PK Parameter	PK_T1	Summary of Statistical Analysis of GSK3342830 Single Dose Plasma Pharmacokinetic Parameters in Part 1 and Part 3 Subjects		SAC [1]

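### The Gamma(1, iscale=5) prior on residual precision, not the data, sets the width of the Part 1 Bayesian predictions, and no prior sensitivity analysis is planned

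*SAP*

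**What the plan says.** SAP 8.2.2 fits log PK parameter on log dose with independent priors (Table 9): Normal with precision 10^-6 for the intercept, half-normal with precision 10^-5 for the slope, and Gamma(1, iscale=5) for the residual precision v = 1/σ². The justification is "Due to limited information available about the GSK3342830 compound, an informative prior with large variance will be used". On the third prior the SAP adds "Furthermore, the scale and shape parameters of the precision prior Gamma function are chosen to attain" a mean of 0.2 and a variance of 0.04.

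The outputs that depend on σ are planned outputs. "The Bayesian predictive probability that an individual subject will have AUC[0-t] and Cmax values greater than" 3460 h·µg/mL and 2590 µg/mL is to be produced for every Part 1 dose. SAP 10.11.7 lists Table 3.18, "Summary of PK Parameters for Part 1 - Bayesian Predictive Probability", as a dose-escalation deliverable. Protocol 4.1 says the predictive probabilities, with safety data, drive escalation decisions.

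Under "Sensitivity and Supportive Statistical Analyses" the SAP 8.2.2 entry is Not applicable. SAP 8.2.3 allows logged deviations, and its example for priors is "changes in the prior structure to support convergence of the parameter estimations in SAS".

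**The concern.** A precision prior with a small mean and a small variance is a confident statement that residual scatter is large, which is the opposite of letting a few subjects per cohort speak. The intercept and slope priors are flat enough that predicted centres follow the data. Predictive widths and individual exceedance probabilities depend on σ, and σ is pulled towards the prior.

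The team deciding on escalation would then see intervals and probabilities that look like summaries of observed variability but barely respond to it. The listed diagnostics (Gelman-Rubin, MCMC error, autocorrelation, trace plots, residual patterns) would all pass with an inflated σ.

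**Working it through.** **Inputs.** Prior: SAP Table 9. Planned active subjects: about 6 per Part 1 cohort, 36 in all (Protocol 4.3). An escalation may rest on "approximately 4 subjects who received active treatment in the previous cohort". Medians and percentiles: protocol Appendix 9, Table 8. Table 8 was simulated from a model adapted from a similar compound, so I take its log-SD as the low end and use 0.20, 0.30 and 0.50 as assumed alternatives.

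**1. The stated moments.** Shape 1 and rate 5 give mean 1/5 = 0.2 and variance 1/25 = 0.04, matching the SAP. Converted to σ = v^(-1/2), the prior 5th, 50th and 95th percentiles are 1.29, 2.69 and 9.87. The prior probability that σ ≤ 0.5 is 2×10^-9.

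**2. The log-SD the protocol expects.** ln(P95/P5)/(2×1.645) for AUC gives 0.134 to 0.136 across the six doses; at 6000 mg, ln(1933/1236)/3.29 = 0.136. The precision is 1/0.136² = 54, which lies (54−0.2)/0.2 ≈ 270 prior SDs above the prior mean. Even log-SD 0.50 (precision 4) is 19 prior SDs above it.

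**3. Weight of the prior.** With effectively flat intercept and slope priors, the posterior of v is Gamma(A, B), where A = 1+(n−2)/2, B = 5+RSS/2 and RSS = (n−2)·SD². The prior's share of the rate is 5/B.

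| log-SD | n=22 | n=30 | n=36 | n for a 50% share = 2+10/SD² |
|---|---|---|---|---|
| 0.136 | 96% | 95% | 94% | 543 |
| 0.30 | 85% | 80% | 77% | 113 |
| 0.50 | 67% | 59% | 54% | 42 |

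**4. Effect on the predictions.** A new subject's log AUC is Student-t with 2A degrees of freedom and scale² = (B/A)(1+h), where h is the leverage of the target log-dose. The 90% factor is exp(t(0.95, 2A)·scale).

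Worked case: five cohorts of 6, target 6000 mg, log-SD 0.136. A = 15, B = 5+28×0.136²/2 = 5.259, h = 0.145, scale = √(0.3506×1.145) = 0.634. The line through the Table 8 medians predicts 1539. Then ln(3460/1539)/0.634 = 1.28 on 30 df, giving P = 10.5%. Under Gamma(0.001, 0.001) the scale is 0.146 and P = 0.0003%.

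Each cell below gives the SAP prior, then the weak prior.

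| Quantity | log-SD 0.136 | 0.20 | 0.30 | 0.50 |
|---|---|---|---|---|
| P(individual AUC>3460), 6000 mg, cohorts 6+6+6+6+6 | 10.5% / 0.0003% | 11.2% / 0.04% | 12.5% / 0.9% | 16.1% / 7.1% |
| Same, cohorts 6+6+6+6+4 | 11.7% / 0.0005% | 12.3% / 0.05% | 13.6% / 1.0% | 17.0% / 7.4% |
| Same, 4000 mg, cohorts 6+6+6+4 | 6.9% / 0.00001% | 7.3% / 0.002% | 8.2% / 0.1% | 10.7% / 2.4% |
| 90% predictive factor (×/÷), 6000 mg, n=30 | 2.93 / 1.28 | 3.02 / 1.44 | 3.23 / 1.73 | 3.92 / 2.48 |
| Posterior mean σ, n=30 | 0.61 / 0.14 | 0.63 / 0.21 | 0.66 / 0.31 | 0.77 / 0.51 |

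The two priors come together only at high variability: at 6000 mg with n=30, 21.9% against 17.6% at log-SD 0.8, and 25.3% against 22.8% at 1.0.

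**5. Checks on the closed form.** A Gibbs run with the exact SAP priors (n=30, log-SD 0.136, 6000 mg) gave 10.6%. In 4,000 simulated datasets the median (10th to 90th percentile) under the SAP prior was 10.5% (8.8 to 12.4) at log-SD 0.136, 12.6% (8.8 to 17.3) at 0.30 and 16.1% (9.8 to 24.7) at 0.50.

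**6. Part 2, same prior.** With 8+8 active subjects at 1000 and 2000 mg TID and log-SD 0.136, the fitted median at 4000 mg TID is 3036. P(individual AUC(0-24)>3460) is 45% against 23% under the weak prior, and P(geometric mean>2875) is 53% against 69%. This is a two-dose fit, which may be excluded because the SAP says the relationship is "characterized by a power model once data are available from 3 dose levels".

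**The case against.** The main points on the other side are these.

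- **Advisory use.** SAP 3.1 says the probabilities may be calculated to help dose selection. There is no cut-off, and protocol Table 1, the 3-fold cap and observed exposures also bound escalation. This stands; no formal rule fails.
- **Direction.** In Part 1 the error overstates exceedance, which is cautious. This stands. In Part 2 the mean-exceedance probability can move the other way, but that depends on whether the mean is read as geometric or arithmetic, so I make no general claim of under-protection.
- **Other outputs move little.** At 6000 mg with n=30 under the SAP prior, P(individual Cmax>2590) is 2.0%, 2.8% and 4.9% at log-SD 0.16, 0.30 and 0.50. P(geometric mean AUC>2875) is 0.5% at log-SD 0.136 and 1.9% at 0.50. These are inflated but small. The material distortion is in individual AUC and the interval widths.
- **The conflict could be noticed.** Maximum-likelihood estimates serve as starting values, the posterior precision is tabulated (Tables 3.14 and 3.15), observed data are overlaid on the curve, and observed means sit beside predictive percentiles in Table 3.16. The poor-fit signs in 8.2.2 and the deviations in 8.2.3 are also open lists. All true, but none is a planned comparison of prior with data.
- **The benchmark is uncertain.** Table 8 is not observed data on this compound. The result does not rest on it: at log-SD 0.50, nearly four times larger, the prior still holds more than half the weight at all 36 subjects.

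**Conclusion.** The concern holds. The precision prior contradicts its stated rationale. At the planned Part 1 size it supplies 54% to 96% of the posterior rate across log-SDs of 0.136 to 0.50 and n of 22 to 36. P(individual AUC>3460) at 6000 mg ranges only from 10.5% to 16.1% over those log-SDs, when a weak prior would give 0.0003% to 7.1%. The 90% predictive factor is 2.93 to 3.92, not 1.28 to 2.48.

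This assumes Table 8 medians, about 6 active subjects per cohort and a true log-SD within that range; the discrepancy largely closes at 0.8 to 1.0. Centres and slope are unaffected, as is the final dose-proportionality analysis, which uses REML. The defect is misleading error bars in an advisory analysis. It should be fixed before the escalation outputs are used.

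**What to change.** In SAP Table 9, replace Gamma(1, iscale=5) with a prior that is weak on the log-PK scale, for example half-normal on σ with scale about 0.5, or Gamma(0.001, iscale=0.001). Revise the sentence on the Gamma moments to match.

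Before use, simulate from protocol Table 8 and confirm that σ is recovered at the planned cohort sizes. At n=30, half-normal(0.5) gives posterior mean σ of 0.142, 0.209, 0.312 and 0.513 for true values 0.136, 0.20, 0.30 and 0.50, and 0.97 for a true 1.0, so it does not suppress large variability.

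Replace the Not applicable sensitivity entry with the exceedance probabilities under at least one alternative precision prior, shown beside the main results.

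The cost is a few lines of SAP text and a small change to the SAS program.

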### Model Checking & Diagnostics

The Gibbs sampling chains will be run using the following conventions:

1. The burn-in period, the number of iterations judged necessary for the Markov Chain Monte Carlo (MCMC) algorithm to achieve convergence, will be assessed after each 5,000 iteration increment until convergence is achieved. Convergence of the chains to the posterior distribution will be assessed using:
  - Gelman-Rubin statistic
  - MCMC error of the chains
  - Autocorrelation plot to assess autocorrelation within each chain
  - Visual inspection of the chain trace plots for proper chain mixing after the application of thinning
2. The burn-in samples must meet all the following convergence criteria, before we accept

### Bayesian Statistical Analyses

the MCMC output as a sample from the posterior distribution:

- 1) The Gelman-Rubin statistic will indicate convergence provided the Brooks-Gelman Ratio (Brooks and Gelman 1998) for all parameters is within the interval (0.8, 1.2). The SAS procedure diagnostic tool will generate the necessary output.
- 2) All MCMC chains will be run until each parameter has estimated MCMC error of less than 5% of its associated standard deviation. This calculation will be performed as the ratio of the MCMC error divided by the parameter's estimated posterior standard deviation.
- 3) Autocorrelation plots will be generated for all chains and accepted provided the estimated autocorrelation for each chain is within  $\pm 0.10$  by lag 10. In the event that any chain's autocorrelations for any one parameter are outside that range after 10 iterations, the number of iterations will be increased by 5000.
- 4) All chains' trace plots will be inspected visually, to assess the mixing of each chain. Convergence is indicated when all chains appear to be mixing well (to be clear: No chain's convergence is indicated until the chains of all model parameters appear well-mixed). Mixing is defined as "each chain is sampling independently values similar to those the other chains have sampled." This will appear in the trace plots as all chains overlapping each other randomly.

The burn-in period will end at the iteration which convergence is reached as determined using the above criteria. Upon convergence a sample size of 10,000 will be obtained from the posterior from each chain. Estimated density plots will be created and inspected for smoothness. If the estimated density plots are not smooth, then an additional sample size of 10,000 iterations, 10,000 from each chain, will be gathered until the estimated density plots are smooth. Estimates for each parameter will include mean, standard deviation, MCMC error, median, and the centred 90% credible sets (the 5th and 95th percentiles) along with the estimated MCMC error for the chain. We will also obtain the Deviance Information Criteria for the model and display this with the associated output.

Poor fit for the model will be indicated by the following, possibly among other findings:

- 1) Patterns in the residuals.
- 2) The model requires more than 10,000 iterations for the burn-in period, after thinning, and an acceptable reparameterisation of the model is not found or it is determined that the chains will not reach convergence.

